**6.1.2 Sample size calculations for serum and mucosal levels**

One of the primary objectives of the study includes assessing the association between the levels of VRC07-523LS measured in serum and in mucosal secretions and tissues at various sites. Measurements will be collected in all 24 participants before the first infusion as well as at several timepoints following the first infusion. The primary statistical analysis will estimate associations between blood and mucosal levels within timepoints. These primary analyses will be conducted irrespective of dose (ie, data from Groups 1 and 2 will be combined) as well as within each treatment group. Additional analyses, secondary in nature, will evaluate association between the levels of VRC07-523LS in serum and in mucosal samples within each birth sex.

The power of the study to detect a significant association between the levels of VRC07-523LS (possibly transformed) measured in serum and in any given mucosa site is shown in [Table 6-3](#) for several values of Pearson’s linear correlation coefficient (r) and sample sizes (n). We anticipate that the primary correlation analysis will be based on samples of sizes n = 12 and n = 24. The secondary correlation analysis will be performed on samples of sizes that are expected to range between n = 5 and n = 15.

In an analysis combining all 24 participants from Groups 1 and 2, the study has more than 72% power to detect a significant association between measurements if the true value of the correlation coefficient is 0.5 or higher. If the true value of the correlation coefficient is 0.6 or higher, the power of the study is greater than or equal to 89.8%.

With 12 participants (eg, in any primary analysis assessing association within a particular treatment group, or in any secondary analysis within a particular birth sex combining both groups), the study has almost 77% power to detect a significant association between measurements if the true value of the correlation coefficient is 0.7 or higher.

With 6 participants (as in any secondary correlation analysis restricted to a specific sex assigned at birth and conducted within a particular treatment group, assuming balance in treatment groups), the study has more than 77% power to

detect a significant association between measurements if the true value of the correlation coefficient is 0.9 or higher.

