## 9.6 Mucosal sampling

Mucosal secretion and biopsy samples will be collected at the timepoints indicated in [Appendix D](#). All participants in this trial will have consented to mucosal specimen collections. Participants assigned male sex at birth will provide semen, rectal secretions, and rectal biopsies. Participants assigned female sex at birth will provide cervicovaginal and rectal secretions, as well as cervical, vaginal and rectal biopsies. Small (~2-4 mm) tissue biopsies are obtained from the vagina and ectocervix using a speculum and from the rectum by anoscopy by experienced clinicians. The product administration and biopsy collection schedules per mucosal compartment and visit are described in detail in [Table 9-1](#), and also outlined in [Appendix D](#); however, fewer samples may be taken based on the judgment of the performing clinician. The number of biopsies collected per mucosal compartment and visit is shown in [Table 9-2](#). Following the first product administration, a participant may decline all or some of the mucosal biopsies or secretion collections, but they should be encouraged to continue with any collections that they deem acceptable until the end of the trial.

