7 STATISTICAL ANALYSIS

This section describes the final study analyses, unblinded as to treatment arm assignment. All analyses pertaining to safety and drug levels objectives of the study will be conducted with an intent-to-treat analysis that includes all randomized individuals per their randomization allocation. Additional analyses will be performed that account for the actual infusions and dose levels that each participant received. Analyses for primary endpoints will be performed using SAS and R. Additional software may be used to perform non-compartmental PK and population PK analyses (eg, Monolix). All other descriptive and inferential statistical analyses will be performed using SAS, or R statistical software.

No formal multiple comparison adjustments will be employed for multiple primary or secondary endpoints. Unless otherwise noted, all statistical tests will be 2-sided and will be considered statistically significant if $p < 0.05$.

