Comparisons of dose-amount-adjusted, IgG-normalized VRC07-523LS concentrations between visits (v2 vs. v5, v2 vs. v7, v2 vs. v9, v4 vs. v6, v4 vs. v8, v6 vs. v8) are made using the Wilcoxon Signed-Rank test, and comparisons between sexes at birth at visits 4 and 5 are made using the Wilcoxon Rank Sum test. Additionally, comparisons of body-weight-adjusted, IgG-normalized VRC07-523LS concentrations between treatment arms at visits 4 and 5 are made using the Wilcoxon Rank Sum test. Comparisons are made for the % penetration of protein-normalized VRC07-523LS between visits, and specimen types using Wilcoxon Signed-Rank test; and between treatment arms using Wilcoxon Rank Sum test; and between sex at birth, controlling for treatment arms using Van Elteren Test. Comparisons are conducted between levels normalized using actual total protein concentrations and those normalized using the U.S. reference protein concentration (70 g/L) with treatment arms (T1 and T2) pooled using the Wilcoxon Signed Rank Test. Linear mixed-effect regression analyses are performed modeling natural log-transformed concentrations as a function of time since most recent infusion, sex at birth, and treatment group. Linear regressions are performed modeling the difference between natural log-transformed concentrations between visits adjusting for the difference between number of days since last infusion at compared visits, as well as sex at birth and treatment group. P-values are adjusted for multiple comparisons by controlling the false discovery rate (FDR) using the Benjamini-Hochberg procedure [9]

and the q-value [10]. Results are significant if the adjusted p-value or q-value ≤ 0.05 . Comparisons are conducted for groups with at least 3 data points for paired test and at least 5 for unpaired test.

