- For mucosal tissues, comparisons between visits 4 vs 8 penetration percentages (protein-normalized VRC07-523LS of mucosal divided by serum at Cmax after a different number of infusions) using Wilcoxon signed-rank test, by treatment group and spec type. P-values will be adjusted for multiple comparisons by controlling the false discovery rate (FDR) using the Benjamini-Hochberg (BH) procedure and the q-value. The unadjusted p-values, BH-adjusted p-values, and q-values will be reported.
- For mucosal tissues, comparisons between visits 2 vs 9 penetration percentages (protein-normalized VRC07-523LS of mucosal divided by serum at trough after a different number of infusions) using Wilcoxon signed-rank test, by treatment group and spec type. P-values will be adjusted for multiple comparisons by controlling the false discovery rate (FDR) using the Benjamini-Hochberg (BH) procedure and the q-value. The unadjusted p-values, BH-adjusted p-values, and q-values will be reported.
- For secretions, comparison of penetration percentages (protein-normalized VRC07-523LS of mucosal divided by serum) between treatment groups, using Wilcoxon rank sum test, at visits 4 and 5. P-values will be adjusted for multiple comparisons by controlling the false discovery rate (FDR) using the Benjamini-Hochberg (BH) procedure and the q-value. The unadjusted p-values, BH-adjusted p-values, and q-values will be reported.
- For mucosal tissues, comparison of penetration percentages (protein-normalized VRC07-523LS of mucosal divided by serum) between treatment groups, using Wilcoxon rank sum test, at visit 4. P-values will be adjusted for multiple comparisons by controlling the false discovery rate (FDR) using the Benjamini-Hochberg (BH) procedure and the q-value. The unadjusted p-values, BH-adjusted p-values, and q-values will be reported.
- For rectal secretions, comparison of penetration percentages (protein-normalized VRC07-523LS of mucosal divided by serum) at visits 4 and 5, among different sexes, controlling for treatment arms, using Van Elteren Test. P-values will be adjusted for multiple comparisons by controlling the false discovery rate (FDR) using the Benjamini-Hochberg (BH) procedure and the q-value. The unadjusted p-values, BH-adjusted p-values, and q-values will be reported.

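### The 3-pair minimum for paired Wilcoxon tests admits cells that cannot reach p ≤ 0.05 under the exact test, mainly in the by-arm cervical and vaginal penetration tables

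*SAP*

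**What the plan says.** SAP 8.3 (Statistical methods) sets the entry rule for tests: "Comparisons are conducted for groups with at least 3 data points for paired test and at least 5 for unpaired test". SAP 7 fixes sidedness and level: "all statistical tests will be 2-sided and will be considered statistically significant if" p < 0.05. For the mucosal assay, SAP 8.3 adds "P-values are adjusted for multiple comparisons by controlling the false discovery rate (FDR) using the Benjamini-Hochberg procedure" together with the q-value, and gives the decision rule: "Results are significant if the adjusted p-value or q-value" is at most 0.05. Either measure is therefore enough.

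Most signed-rank tables in SAP 8.3.1 pool the arms or are listed by specimen type only. The two tissue-penetration tables (visit 4 vs 8, visit 2 vs 9) are instead run "using Wilcoxon signed-rank test, by treatment group and spec type".

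Protocol 9.6 limits who contributes female tissue: "Participants assigned female sex at birth will provide cervicovaginal and rectal secretions, as well as cervical, vaginal and rectal biopsies". Protocol 6.1.2 gives the size of a sex-by-arm cell: "With 6 participants (as in any secondary correlation analysis restricted to a specific sex assigned at birth and conducted within a particular treatment group".

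The SAP does not say whether Wilcoxon p-values are exact or asymptotic, does not define the family for each adjustment, and has no rule keeping very small comparisons out of it.

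**The concern.** A minimum sample size for a test should at least let the test reach its own significance level. Three pairs does not, and nor do 4 or 5 under the exact distribution. A comparison of that size carries almost no inferential information, yet it still counts in the multiplicity adjustment. Under BH it raises the bar for every other test in its table, here the rectal comparisons, which have about twice as many pairs. The tables concerned serve the second primary objective and the first secondary objective, which SAP 8.3 assigns to this assay.

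The unnamed p-value version is a further weakness. At 5 pairs, the same data fall on either side of 0.05 depending on the software default.

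**Working it through.** **Inputs from the documents.** Paired minimum 3 (SAP 8.3). Two-sided 0.05 (SAP 7). About 6 participants per sex-by-arm cell (Protocol 6.1.2). Missing data 17% from network experience, or 10–15% of drug concentrations in the earlier VRC01 trial (Protocol 6.1). The documents give no power figure for these Wilcoxon tests, so there is none to reproduce.

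**Step 1: smallest attainable p-value.** The most extreme result has all n differences of one sign. Its exact two-sided p is 2/2^n.

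| Pairs | Exact | Normal, continuity-corrected | Normal, uncorrected |
|---|---|---|---|
| 3 | 0.25 | 0.181 | 0.109 |
| 4 | 0.125 | 0.100 | 0.068 |
| 5 | 0.0625 | 0.059 | 0.043 |
| 6 | 0.03125 | 0.036 | 0.028 |

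Three and 4 pairs fail in every version. Five pairs pass only in the last column. Six is the first size that passes in all three.

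**Step 2: how often a planned cell of 6 falls to 5 or fewer.** With missing rate d, the chance is 1 − (1 − d)^6 if data are lost by participant. If each of the two samples can be lost independently, it is 1 − (1 − d)^12.

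- d = 10%: 1 − 0.9^6 = 0.47 by participant; 1 − 0.9^12 = 0.72 by sample.
- d = 17%: 1 − 0.83^6 = 0.67 by participant; 1 − 0.83^12 = 0.89 by sample.

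The expected number of pairs runs from 6 × 0.9 = 5.4 down to 6 × 0.83² = 4.1. With 12 planned pairs the chance of 5 or fewer is at most 4.7%; with 24 it is essentially zero.

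**Step 3: cost under BH.** Assumed family: one tissue table, 3 specimen types × 2 arms = 6 tests, of which 2 are rectal and 4 are cervical or vaginal with 5 pairs. A BH-adjusted p is never below the raw p, so with exact p-values the 5-pair tests cannot reject. The first BH threshold is 0.05/6 = 0.0083 with all six tests and 0.05/2 = 0.025 with the two rectal tests alone. When both rectal tests reject, the larger must be at most 2 × 0.05/6 = 0.0167, against 0.05. Simulated BH power per rectal test (exact signed-rank, normal differences):

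| Rectal pairs, effect | All six | Rectal only |
|---|---|---|
| 8, 0.8 SD | 0.18 | 0.37 |
| 10, 1 SD | 0.46 | 0.75 |
| 12, 1 SD | 0.66 | 0.83 |

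**Step 4: the SAP's 'or' rule.** The q-value multiplies the BH value by an estimate of the proportion of true nulls, π0. Assume Storey's estimator at λ = 0.5, floored at one over the number of tests. With 10 rectal pairs and 1 SD:

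| Small tests | Rectal power, all six | Rectal power, rectal only | 5-pair tests declared significant |
|---|---|---|---|
| True nulls | 0.57 | 0.85 | 3% |
| Real 1 SD effect | 0.90 | 0.85 | 64% |

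Every one of those 5-pair declarations has raw p of at least 0.0625. A worked case: p = 0.0005, 0.001, 0.002, 0.004, 0.0625, 0.6. One value exceeds 0.5, so π0 = 1/(6 × 0.5) = 0.33. For p = 0.0625 the BH value is 0.0625 × 6/5 = 0.075, and q = 0.33 × 0.075 = 0.025, which the SAP calls significant.

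**The case against.** The strongest objection is that the SAP does not decide on BH alone. A reader might infer that tests on 3 to 5 pairs can never be significant and always cost the rectal tests power. The documents do not support that. The q-value is an equal route to significance, no p-value version is named, and when the small tests carry real effects rectal power does not fall (0.90 vs 0.85). This stands, and it limits the claim. It does not rescue the minimum, because the q-value route calls results significant whose raw p exceeds 0.05, using a π0 estimated from six p-values. Without the assumed floor, π0 is zero whenever no p-value exceeds 0.5, and then everything is declared significant.

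Second, most of the BH loss comes from family size. This also stands. A 6-pair test passes BH only if its rank k among m tests satisfies k/m ≥ 0.03125/0.05 = 0.625, that is rank 4 or higher of 6. Four such tests give rectal BH power of 0.46 if null and 0.53 with a 1 SD effect, still below 0.75. The difference is that a 6-pair test can reject, so its cost buys something.

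Third, the six-test family, the rectal pair counts and the effect sizes are assumptions. That is correct. The range is shown for this reason, and no single figure should be read as a property of the trial.

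Fourth, the scope is narrow. With complete data and balanced sexes, no planned paired cell is below 6. Protocol 6.4.4.1 already warns of limited power, and SAP 8.3.1 reports unadjusted p-values beside the adjusted ones. This softens the consequence but leaves the entry rule as it is.

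**Conclusion.** The point holds in a limited form. The paired minimum is too low for a two-sided 0.05 test. With exact p-values this is arithmetic for 3, 4 and 5 pairs; for 5 pairs it depends on the version, which the SAP should name.

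The practical reach is the by-arm cervical and vaginal penetration tables, where 5 or fewer pairs has a 47–89% chance under the protocol's own missing-data figures. The consequence depends on the route. Under BH these tests cannot reject, and they lower rectal power by roughly 0.17 to 0.29 in the assumed scenarios. Under the q-value criterion the loss persists if the small tests are null (0.57 vs 0.85) and disappears if they are not, but tests with raw p above 0.05 can be declared significant.

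These sizes rest on treating each table as one family, on the assumed effects and pair counts, and on λ = 0.5 with a floored π0. The change is worthwhile because neither route makes good use of cells this small. It does not threaten the trial's main conclusions.

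**What to change.** Replace the entry rule in SAP 8.3 with one that:

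- requires at least 6 non-zero paired differences for a signed-rank test;
- specifies exact p-values;
- reports smaller cells descriptively (individual values, median, range) and leaves them out of the false-discovery adjustment;
- treats each table in SAP 8.3.1 as its own family.

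The exclusion must depend on pair count only, never on observed p-values.

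Two related wordings should be settled in the same edit. First, state whether the BH value or the q-value decides, since the new minimum alone does not stop a q-value from falling below a raw p above 0.05. Second, reconcile the adjustment in 8.3 with SAP 7, which says "No formal multiple comparison adjustments will be employed for multiple primary or secondary endpoints".

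The cost is a short text change with no effect on data collection. A few female-tissue cells become descriptive, and 6-pair tests kept in a family still carry a multiplicity cost.

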8.3.1 List of Tables

- Comparisons of body weight at baseline (T1: VRC07-523LS 10 mg/kg vs T2: VRC07-523LS 30 mg/kg) using Wilcoxon Rank Sum Test, by sex at birth.
- Comparisons of body weight at baseline (Female vs Male) using Wilcoxon Rank Sum Test, by arm.
- Summary statistics (i.e., N, min, 25%ile, mean, median, 75%ile, max, geometric mean, standard deviation) of body-weight-adjusted IgG-normalized VRC07-523LS concentration for each specimen type, by specimen type, treatment arm, assigned sex at birth and visit.
- Summary statistics (i.e., N, min, 25%ile, mean, median, 75%ile, max, geometric mean, standard deviation) of body-weight-adjusted protein-normalized VRC07-523LS concentration for each specimen type, by specimen type, treatment arm, assigned sex at birth and visit.
- For secretions, dose normalized IgG-normalized VRC07-523LS concentrations comparisons between visits 4, 6, and 8 (Cmax after a different number of infusions) using Wilcoxon signed-rank test, by specimen type. P-values will be adjusted for multiple comparisons by controlling the false discovery rate (FDR) using the Benjamini-Hochberg (BH) procedure and the q-value. The unadjusted p-values, BH-adjusted p-values, and q-values will be reported.
- For secretions, dose normalized IgG-normalized VRC07-523LS concentrations comparisons between visits 2, 5, 7, and 9 (trough after a different number of infusions) using Wilcoxon signed-rank test, by specimen type. P-values will be adjusted for multiple comparisons by controlling the false discovery rate (FDR) using the Benjamini-Hochberg (BH) procedure and the q-value. The unadjusted p-values, BH-adjusted p-values, and q-values will be reported.
- For mucosal tissues, comparisons between visits 4 vs 8 dose normalized IgG-normalized VRC07-523LS concentrations (Cmax after a different number of infusions) using Wilcoxon

signed-rank test, by specimen type. P-values will be adjusted for multiple comparisons by controlling the false discovery rate (FDR) using the Benjamini-Hochberg (BH) procedure and the q-value. The unadjusted p-values, BH-adjusted p-values, and q-values will be reported.

- For mucosal tissues, comparisons between visits 2 vs 9 dose normalized IgG-normalized VRC07-523LS concentrations (trough after a different number of infusions) using Wilcoxon signed-rank test, by specimen type. P-values will be adjusted for multiple comparisons by controlling the false discovery rate (FDR) using the Benjamini-Hochberg (BH) procedure and the q-value. The unadjusted p-values, BH-adjusted p-values, and q-values will be reported.
- For secretions, body-weight-adjusted IgG-normalized VRC07-523LS concentrations comparisons between treatment groups at visits 4 and 5 using Wilcoxon signed-rank test, by specimen type with sex at birth combined. P-values will be adjusted for multiple comparisons by controlling the false discovery rate (FDR) using the Benjamini-Hochberg (BH) procedure and the q-value. The unadjusted p-values, BH-adjusted p-values, and q-values will be reported.
- For mucosal tissues, body-weight-adjusted IgG-normalized VRC07-523LS concentrations comparisons between treatment groups at visit 4 using Wilcoxon signed-rank test, by specimen type with sex at birth combined. P-values will be adjusted for multiple comparisons by controlling the false discovery rate (FDR) using the Benjamini-Hochberg (BH) procedure and the q-value. The unadjusted p-values, BH-adjusted p-values, and q-values will be reported.
- Comparisons for body-weight-adjusted IgG-normalized VRC07-523LS concentration at peak timepoints (T1 vs T2) using Wilcoxon rank sum test, by specimen type and for (1) both assigned sexes at birth combined for rectal biopsies and rectal secretions and (2) each assigned sex at birth separately for other specimen types. P-values will be adjusted for multiple comparisons by controlling the false discovery rate (FDR) using the Benjamini-Hochberg (BH) procedure and the q-value. The unadjusted p-values, BH-adjusted p-values, and q-values will be reported.
- For rectal secretions, dose-amount-adjusted IgG-normalized VRC07-523LS concentrations comparisons at visit 4 and 5 among different sexes, using Wilcoxon rank sum test, by specimen type. P-values will be adjusted for multiple comparisons by controlling the false discovery rate (FDR) using the Benjamini-Hochberg (BH) procedure and the q-value. The unadjusted p-values, BH-adjusted p-values, and q-values will be reported.
- For rectal biopsies, dose-amount-adjusted IgG-normalized VRC07-523LS concentrations comparisons at visit 4 among different sexes, using Wilcoxon rank sum test, by specimen type. P-values will be adjusted for multiple comparisons by controlling the false discovery rate (FDR) using the Benjamini-Hochberg (BH) procedure and the q-value. The unadjusted p-values, BH-adjusted p-values, and q-values will be reported.
- Specimen comparison using partial Spearman's rank correlation, adjusted for treatment arms (T1 and T2) and sex assigned at birth, stratified by visit. P-values will be adjusted for multiple comparisons by controlling the false discovery rate (FDR) using the Benjamini-Hochberg (BH) procedure and the q-value. The unadjusted p-values, BH-adjusted p-values, and q-values will be reported.
- Summary of the percentage of penetration for protein-normalized VRC07-523LS concentration, by specimen type, treatment arm, assigned sex at birth and visit.
- For secretions, comparisons between visits 4, 6, and 8 penetration percentages (protein-normalized VRC07-523LS of mucosal divided by serum at Cmax after a different number of infusions) using Wilcoxon signed-rank test, by specimen types with treatment groups combined. P-values will be adjusted for multiple comparisons by controlling the false

discovery rate (FDR) using the Benjamini-Hochberg (BH) procedure and the q-value. The unadjusted p-values, BH-adjusted p-values, and q-values will be reported.

- For secretions, comparisons between visits 2, 5, 7, and 9 penetration percentages (protein-normalized VRC07-523LS of mucosal divided by serum at trough after a different number of infusions after a different number of infusions) using Wilcoxon signed-rank test, by specimen types with treatment groups combined. P-values will be adjusted for multiple comparisons by controlling the false discovery rate (FDR) using the Benjamini-Hochberg (BH) procedure and the q-value. The unadjusted p-values, BH-adjusted p-values, and q-values will be reported.
- For mucosal tissues, comparisons between visits 4 vs 8 penetration percentages (protein-normalized VRC07-523LS of mucosal divided by serum at Cmax after a different number of infusions) using Wilcoxon signed-rank test, by treatment group and spec type. P-values will be adjusted for multiple comparisons by controlling the false discovery rate (FDR) using the Benjamini-Hochberg (BH) procedure and the q-value. The unadjusted p-values, BH-adjusted p-values, and q-values will be reported.
- For mucosal tissues, comparisons between visits 2 vs 9 penetration percentages (protein-normalized VRC07-523LS of mucosal divided by serum at trough after a different number of infusions) using Wilcoxon signed-rank test, by treatment group and spec type. P-values will be adjusted for multiple comparisons by controlling the false discovery rate (FDR) using the Benjamini-Hochberg (BH) procedure and the q-value. The unadjusted p-values, BH-adjusted p-values, and q-values will be reported.
- For secretions, comparison of penetration percentages (protein-normalized VRC07-523LS of mucosal divided by serum) between treatment groups, using Wilcoxon rank sum test, at visits 4 and 5. P-values will be adjusted for multiple comparisons by controlling the false discovery rate (FDR) using the Benjamini-Hochberg (BH) procedure and the q-value. The unadjusted p-values, BH-adjusted p-values, and q-values will be reported.
- For mucosal tissues, comparison of penetration percentages (protein-normalized VRC07-523LS of mucosal divided by serum) between treatment groups, using Wilcoxon rank sum test, at visit 4. P-values will be adjusted for multiple comparisons by controlling the false discovery rate (FDR) using the Benjamini-Hochberg (BH) procedure and the q-value. The unadjusted p-values, BH-adjusted p-values, and q-values will be reported.
- For rectal secretions, comparison of penetration percentages (protein-normalized VRC07-523LS of mucosal divided by serum) at visits 4 and 5, among different sexes, controlling for treatment arms, using Van Elteren Test. P-values will be adjusted for multiple comparisons by controlling the false discovery rate (FDR) using the Benjamini-Hochberg (BH) procedure and the q-value. The unadjusted p-values, BH-adjusted p-values, and q-values will be reported.
- For rectal biopsies, comparison of penetration percentages (protein-normalized VRC07-523LS of mucosal divided by serum) at visit 4, among different sexes, controlling for treatment arms, using Van Elteren Test. P-values will be adjusted for multiple comparisons by controlling the false discovery rate (FDR) using the Benjamini-Hochberg (BH) procedure and the q-value. The unadjusted p-values, BH-adjusted p-values, and q-values will be reported.
- Among females, comparison of penetration percentages (protein-normalized VRC07-523LS of mucosal divided by serum) at visits 4 and 5 for rectal biopsies vs cervical biopsies, rectal biopsies vs vaginal biopsies, cervical biopsies vs vaginal biopsies, and rectal secretions vs cervicovaginal secretions, using Wilcoxon signed-rank test, with treatment arms combined, by visit. P-values will be adjusted for multiple comparisons by controlling the false discovery rate (FDR) using the Benjamini-Hochberg (BH) procedure and the q-value. The unadjusted p-values, BH-adjusted p-values, and q-values will be reported.

- Among males, comparison of penetration percentages (protein-normalized VRC07-523LS of mucosal divided by serum) at visit 4 for rectal secretions vs semen, using Wilcoxon signed-rank test, with treatment arms combined, by visit. P-values will be adjusted for multiple comparisons by controlling the false discovery rate (FDR) using the Benjamini-Hochberg (BH) procedure and the q-value. The unadjusted p-values, BH-adjusted p-values, and q-values will be reported.
- Comparisons for dose-amount-adjusted protein-normalized VRC07523LS levels in serum between actual total protein levels and U.S. reference protein levels (70 g/L) with T1+T2 pooled using Wilcoxon signed rank test, by specimen type and visit. P-values will be adjusted for multiple comparisons by controlling the false discovery rate (FDR) using the Benjamini-Hochberg (BH) procedure and the q-value. The unadjusted p-values, BH-adjusted p-values, and q-values will be reported.
- Analysis of the impact of time since the most recent infusion, sex at birth, and treatment on log-transformed, body-weight-adjusted IgG-normalized VRC07523LS levels across specimen types using a linear mixed-effects model. P-values will be adjusted for multiple comparisons by controlling the false discovery rate (FDR) using the Benjamini-Hochberg (BH) procedure and the q-value. The unadjusted p-values, BH-adjusted p-values, and q-values will be reported.
- Analysis of the impact of time difference between visits since the most recent infusion, sex at birth, and treatment on log-transformed, body-weight-adjusted IgG-normalized VRC07523LS levels across specimen types using a linear regression model. P-values will be adjusted for multiple comparisons by controlling the false discovery rate (FDR) using the Benjamini-Hochberg (BH) procedure and the q-value. The unadjusted p-values, BH-adjusted p-values, and q-values will be reported.

